Approval Date: 21st November, 2022

**DOES PERI-OPERATIVE PARENTERAL NUTRITION
AFFECT OUTCOME IN PATIENTS UNDERGOING MAJOR
ABDOMINAL SURGERIES**

NEPAL MEDICAL COLLEGE

SUBMITTED BY

[name]. [name]

Head of Department

Department of Surgical Gastroenterology

Nepal Medical College, [name]

RESEARCH DESIGN:

Type of study: Retrospective observational study

Place of study: Department of Surgical Gastroenterology, Nepal Medical College and Teaching Hospital, [name].

Duration of study: 2017, January 1st to 2022, August 31st (5 years 7 months)

Sampling technique: Consecutive sampling technique

Sample Size:

To select the appropriate sample size, we considered the prevalence of malnutrition in surgical patients to be 24% (3) at a confidence interval of 95% ($Z = 1.96$), and a precision (d) of 7%. Based on these calculations, the sample size obtained was 143.

We obtained the sample size using the following formula:

For large population (infinite population)

$$= 3.84 * 0.24 * 0.76 / (0.07 * 0.07) = 142.9 = 143$$

n = Sample size

$$Z^2 = 1.96 * 1.96 = 3.84$$

$$p = \text{Prevalence value} = 24\% = 0.24$$

$$q = 1 - p = 1 - 0.24 = 0.76$$

$$d = \text{desirable error or precision level (5% to 10\%)} = 7\% = 0.07 \text{ (pre-set value)}$$

Inclusion criteria:

1. All patients who underwent major gastrointestinal surgery after receiving perioperative TPN.

Exclusion criteria:

1. Patient refused to participate.
2. Perioperative TPN was not given as per the protocol.

Ethical consideration:

All patients enrolled in the study were explained about the enrollment, and verbal and written consent were obtained from the patient. Patients were counseled about the strict confidentiality that would be maintained throughout their participation in this study, and that their name would not be disclosed in the proforma or after the completion of study until voluntarily disclosed by the patient. Ethical approval will be obtained from the Institutional Review Committee (IRC) of Nepal Medical College and Teaching Hospital.

Data collection: All patients that undergo major gastroenterological surgeries are always entered in our data sheet maintained by the department. As all the data regarding the hospital stay, course of illness, management and operation procedures are clearly maintained in these data sheets, we will only select those cases who received perioperative TPN. A sample of this data sheet which is also our proforma is shown in Annex I.

Study Procedure:

1. Consent: After obtaining ethical clearance from the IRC, those patients that fulfill the inclusion criteria will be offered detailed printed information about the proposed study. Since this is a retrospective study, phone calls will be done to the patients and their relatives for consent. Patients agreeing to take part in the study will be requested to sign the consent form. After signing the consent, the patient's data will be recruited in this study. There will be no discrimination of sex, race, religion and geography.

2. Nutritional status assessment: All the patients were evaluated for nutritional status by following the ESPEN guidelines¹⁰ at the time of admission. According to the guidelines, the diagnosis of malnutrition is based on two options:

(1) $\text{BMI} < 18.5 \text{ kg/m}^2$,

(2) Combined:

- Weight loss $>10\%$ indefinite of time or $>5\%$ over 3 months and
- Either reduced BMI ($<20 \text{ kg/m}^2$ in younger than 70 or $<22 \text{ kg/m}^2$ in patients older than 70 years) or fat free mass index (FFMI) < 15 in women and 17 in men.

Similarly patients at severe nutritional deficiency risk are defined by presence of one of the following:

(1) Weight loss $>10\text{--}15\%$ within 6 months,

(2) $\text{BMI} < 18.5 \text{ kg/m}^2$, and

(3) Preoperative serum albumin $< 30 \text{ g/L}$ (without evidence of liver or kidney dysfunction).

3. Routes and selection of PN: All the patients who were found to have malnutrition or were at severe risk of nutrition deficiency were given preoperative PN. PN was given as infusion via central venous catheter from the day of admission via central venous catheter.¹¹ The CVC was kept by the anesthesiology team on the day of admission. The PN was available in a standard 3-compartment package developed by BAXTER and comprising lipid, carbohydrate and amino acids with minerals.

4. Duration and dosing of PN: In those patients who required emergency surgery, PN was given in postoperative period until resumption of oral feeding. In non-emergent cases where surgery could be delayed for 5 days, PN was given for 5 days preoperatively based on the fact that our body needs at least 5-7 days to recover its full physiological activity and body protein framework and was continued in the post-operative period until the resumption of enteral feeding. The dosing of PN was based on ESPEN guidelines with total energy of 25-30Kcal/kg/day and 1.2g/kg/day of proteins.
5. Intraoperative and postoperative status: All patients underwent surgery after preoperative assessment on 5th day onwards of admission. All the surgeries were done by the same team of surgeons. The intraoperative events were recorded by taking in consideration the anesthesiology chart. Postoperatively their progress as well as outcome were filled in the datasheet everyday till discharge.
6. Complications: The complications faced by the patient were graded according to the Clavien-Dindo Classification system¹² by keeping records till 30 days of the surgical procedure date.

Data Analysis Technique: Data collected on a hard copy proforma will be entered and analyzed in Microsoft excel and into IBM- Statistical Package for the Social Sciences (SPSS) version 16.0 respectively. Continuous variables will be expressed as the mean value + or - standard deviation (SD) and range, while categorical variables will be expressed as proportions. We will use the chi-square test and the exact test of Fischer for analysis of categorical data and univariate

linear regression analysis to show association. The data, after analysis, will be reported with descriptive statistics, with all data reported as mean \pm SD, and the final result will be compared with various studies listed in the Literature Review section. Various frequency tables, charts, graphs, trends, plots and bar diagrams will be used to present the data.

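### The 143 patients and 7-point precision are computed for malnutrition prevalence in surgical patients, which a TPN-only cohort cannot estimate; the complications and planned tests have no stated precision

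*Combined protocol and SAP*

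**What the plan says.** The Sample Size section takes a malnutrition prevalence ("we considered the prevalence of malnutrition in surgical patients to be 24" per cent), 95% confidence and a precision of 7 points. It concludes: "Based on these calculations, the sample size obtained was 143". This is the only statement of size or precision in the supplied text.

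The cohort is narrower than surgical patients in general. The inclusion criterion is "All patients who underwent major gastrointestinal surgery after receiving perioperative TPN". The Data collection section explains that the department's data sheet holds all major cases, but "we will only select those cases who received perioperative TPN". Study Procedure item 3 says that preoperative PN went to patients who were malnourished or at severe nutritional risk.

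The outcome recorded is complications to 30 days, graded by Clavien-Dindo (Study Procedure item 6). The Data Analysis Technique section plans proportions for categorical variables, chi-square and Fisher exact tests, and univariate linear regression. It gives no expected rate, grouping variable, effect size or power for any of these.

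**The concern.** A prevalence in surgical patients needs surgical patients as its denominator. Here the denominator is TPN recipients, and receipt of preoperative PN depended on nutritional status, which is the very characteristic whose prevalence was used for sizing. The malnourished share of this cohort can be tabulated, since everyone was assessed on admission, but it is a different parameter from the 24%.

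The title asks whether perioperative PN affects outcome. The plan's one precision figure therefore says nothing about what the study will report. A reader who carries the 7 points over to the complication rate could be wrong in either direction. A reader who carries it over to a comparison of two groups would, at most plausible rates, think the result more precise than it is.

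**Working it through.** **1. The plan's own figure.** Inputs from the Sample Size section: Z² = 3.84, p = 0.24, q = 0.76, d = 0.07.

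n = Z²pq/d² = 3.84 × 0.24 × 0.76 / 0.0049 = 142.94, rounded to 143.

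The figure reproduces. (With 1.96² = 3.8416 the result is 143.002, an immaterial difference.)

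**2. What the 7 points belong to.** They are the half-width for a proportion of 24% at n = 143: 1.96 × √(0.24 × 0.76/143) = 7.0 points. They hold at that rate and for a single proportion only.

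**3. A single proportion at N = 143.** The documents give no complication rate, so the rates below are assumed. The normal half-width is 1.96 × √(p(1 − p)/143). The exact half-width is half the Clopper-Pearson interval at the nearest whole count.

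| Assumed rate | Normal (points) | Exact (points, count) |
|---|---|---|
| 10% | 4.9 | 5.2 (14/143) |
| 24% | 7.0 | 7.3 (34/143) |
| 30% | 7.5 | 7.8 (43/143) |
| 50% | 8.2 | 8.5 (71/143) |

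**4. If the actual N is not 143.** The worst case over rates is 1.96 × 0.5 × 100/√N = 98/√N points by the normal approximation. The exact column is the maximum over all counts.

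| Assumed N | Normal worst case | Exact worst case |
|---|---|---|
| 100 | 9.8 | 10.2 |
| 143 | 8.2 | 8.5 |
| 200 | 6.9 | 7.1 |

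**5. A difference between two groups within 143.** No grouping variable is named, so the splits are assumed, with the same rate in both groups. The half-width is 1.96 × √(p(1 − p)(1/n₁ + 1/n₂)).

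| Assumed rate | 72/71 split (points) | 114/29 split (points) |
|---|---|---|
| 5% | 7.1 | 8.9 |
| 10% | 9.8 | 12.2 |
| 15% | 11.7 | 14.6 |
| 24% | 14.0 | 17.4 |
| 50% | 16.4 | 20.4 |

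The low-rate entries are rough because expected events are few. At 5% there are about 3.6 per group with 72/71. The group of 29 expects about 1.5 events at 5% and 2.9 at 10%.

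**6. Whether 143 set the size at all.** Sampling is described as "Consecutive sampling technique", the data window is "2017, January 1st to 2022, August 31st", and the document carries "Approval Date: 21st November, 2022". The window had closed before approval. Inclusion also depends on consent sought afterwards: "phone calls will be done to the patients and their relatives for consent". The number analysed may therefore be the available consenting cases rather than 143, which is why step 4 shows other values of N.

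**The case against.** The strongest objection is that little follows from the mismatch. By the normal approximation, 143 patients give 7 points or better for any single proportion up to 24%. The worst shortfall is 8.2 − 7.0 = 1.2 points (8.5 − 7.0 = 1.5 exact). In a retrospective series of consecutive cases, the number is in any case set by what exists. The Sample Size section also names the quantity that its precision refers to, so a careful reader need not be misled. All of this stands, and it limits the severity.

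The two-group figures rest on assumed rates and splits. Below 5% the half-width can fall under 7 points: 6.4 at 4% with 72/71, and 6.95 at 3% with 114/29, although the approximation is poor there. The plan names its tests without naming groups, so the two-group layout is an illustration. The univariate linear regression is not covered by these figures either.

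Emergency patients received PN after surgery (Study Procedure item 4), and the text does not clearly say that they too were selected on nutritional status. The conclusion does not depend on this, because TPN recipients are not a sample of all surgical patients. A literature review and an annex are mentioned but not supplied, so the point is limited to the text at hand.

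None of this connects 143 or the 7 points to the study's outcomes.

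**Conclusion.** The point holds. The calculation is arithmetically correct but aimed at a parameter that the inclusion criterion puts out of reach, and the supplied text states no precision for the complications or the planned tests.

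At N = 143, the 7 points overstate the uncertainty of a single proportion at low rates and slightly understate it above 24%. For a two-group difference they understate it throughout the assumed range of 5% to 50%, by a factor of more than two at the upper end (16.4/7 = 2.3 for 72/71; 20.4/7 = 2.9 for 114/29). These sizes rest on assumed rates and splits. The mismatch itself needs no assumption.

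The patients, the data and the tests are unaffected. The defect lies in the stated rationale and precision. It should be fixed, and its severity is modest.

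**What to change.** Keep the existing calculation on record and add a sentence such as: *This calculation concerns the prevalence of malnutrition in surgical patients, which this TPN-only cohort cannot estimate; it does not justify the size for the study's outcomes.*

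Name the main outcome. The supplied text names none, and the 30-day complication proportion is the obvious candidate. Report it with a 95% confidence interval at the actual N, and state the interval method. If a worst case is quoted, 98/√N points applies to the normal approximation only; exact intervals are slightly wider. A single-proportion precision does not cover comparisons, so report each chi-square or Fisher comparison of two proportions with the difference, its 95% confidence interval and the method.

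Two additions would help but are not essential. The first is to say whether 143 was a target, a minimum or a cap, or that N is simply the available consenting cases. The second is to give the numbers identified, consenting and included.

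The essential change costs one paragraph and some intervals in the tables, with no new patients or data. The drawback is that the stated precision may look less favourable: up to about 8.2 points (8.5 exact) for a single proportion at N = 143, more if N is smaller, and generally wider for comparisons.

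### Exclusion 2 selects patients partly on postoperative PN adherence, which is settled inside the 30-day complication window, so the reported complication rate may be biased in either direction

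*Combined protocol and SAP*

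**What the plan says.** The cohort is defined by treatment. The inclusion criterion is "All patients who underwent major gastrointestinal surgery after receiving perioperative TPN", and Data collection confirms that "we will only select those cases who received perioperative TPN". The second exclusion criterion removes a patient when "Perioperative TPN was not given as per the protocol". No adherence threshold is given, and neither is a rule for PN stopped early.

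The PN course appears in Study Procedure step 4. For non-emergent cases "PN was given for 5 days preoperatively", and it "was continued in the post-operative period until the resumption of enteral feeding". For emergencies the course is postoperative only: "In those patients who required emergency surgery, PN was given in postoperative period until resumption of oral feeding". Step 4 also sets an energy and a protein dose.

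Step 5 says that every patient had surgery on or after the fifth day of admission, and that progress and outcome were entered daily until discharge. Step 6 grades complications up to 30 days after surgery. The Data Analysis Technique section plans to compare the final result with published studies. No untreated group and no primary outcome are named. The plan describes no count of patients removed by Exclusion 2 and no analysis that includes them.

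**The concern.** Eligibility should rest on facts fixed before outcome follow-up begins. The five preoperative days of PN meet that test. The postoperative part does not. Whether PN ran until feeding resumed, and at the stated dose, becomes known only after surgery, and a complication or death can itself change the answer. Excluding on it can therefore select on outcome.

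This matters more than usual here. With no internal comparison group, any complication rate set against the literature carries whatever selection produced it, and no planned analysis would reveal the selection.

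**Working it through.** **1. When adherence is settled.**
- Preoperative course, 5 days (step 4): known by the time of surgery.
- Postoperative course, until oral or enteral feeding resumes (step 4): known only after surgery.
- Complications (step 6): counted from surgery to day 30.

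The second item overlaps the third. That overlap is the whole of the concern; the preoperative requirement is not part of it.

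**2. Whether outcomes were on file at selection.** The study period ends on 31 August 2022. If the study dates are surgery dates (an assumption), the last 30-day window closes on 30 September 2022. The document is headed "Approval Date: 21st November, 2022". From 30 September to 31 October is 31 days, and to 21 November a further 21, so 52 days in all. Cases are picked from existing departmental sheets after ethical clearance. It is therefore likely, though not stated, that outcomes were available when Exclusion 2 was applied.

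**3. Size of the bias.** Let f be the share excluded, r the complication rate in retained patients, and e the rate in excluded patients.

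Rate in all = (1 − f)r + f·e, so rate in all − reported rate = f(e − r) = f·d.

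The documents give neither f nor d. On assumed values:

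| f | d = +10 points | d = 0 | d = −10 points |
|---|---|---|---|
| 10% | 1.0 too low | 0 | 1.0 too high |
| 20% | 2.0 too low | 0 | 2.0 too high |
| 30% | 3.0 too low | 0 | 3.0 too high |

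Doubling d doubles each entry, so d = ±20 points gives up to 6 points either way at f = 30%. Negative differences are limited because e cannot fall below zero: d = −10 needs r of at least 10%, and d = −20 needs r of at least 20%.

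Another set of assumptions gives the same message. Take a rate of 30% in all treated patients and 20% excluded. If the excluded have twice that rate (60%), the reported rate is (0.30 − 0.20 × 0.60)/0.80 = 22.5%, which is 7.5 points too low. If they have half (15%), it is (0.30 − 0.20 × 0.15)/0.80 = 33.8%, which is 3.8 points too high.

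**4. The plan's own figure.** The sample size reproduces: 3.84 × 0.24 × 0.76/0.0049 = 142.9, so 143. It was set for malnutrition prevalence and says nothing about complications. For scale only, at an assumed rate of 25% the 95% half-width with 143 patients is 1.96 × √(0.25 × 0.75/143) = 7.1 points. A selection bias of 1 to 3 points is smaller than that, but it does not shrink with more patients and no interval would show it.

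**5. Emergency patients.** Step 4 contrasts emergency patients, who receive PN postoperatively, with cases whose surgery could wait 5 days. Step 5 puts every operation on day 5 or later. Both cannot hold as written. The inclusion criterion, read literally, requires PN before surgery and would drop the emergency group. Step 4 and the selection rule under Data collection indicate that these patients are meant to be in.

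**The case against.** The strongest reply is that the harmful route is narrow. Step 4 fixes no postoperative duration. A patient with a leak or ileus who stays on PN longer is adherent, and so, on a natural reading, is one who remains on PN until death. Only PN stopped before feeding resumed, or given below dose, is clearly a deviation. This stands. A reader might infer that the rule strips out deaths and serious complications and so flatters the rate; the documents do not show that. If under-dosed patients were mainly those recovering well, the bias would run the other way.

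A reader might also infer that the investigators apply the exclusion with the outcomes in view. No section says who applies it or in what order the sheet is read. The daily entries run only to discharge, so complications after discharge rest on step 6 alone. Knowledge of outcomes at selection remains a plausible inference and no more.

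The magnitude is wholly assumed, and the range includes zero. That also stands.

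Finally, restricting a descriptive cohort to patients who received a specified regimen can be a legitimate question. It is weaker here because the regimen is completed during outcome follow-up and the terms of adherence are undefined. Defining those terms would help, but would still leave the main estimate conditional on a postoperative event.

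**Conclusion.** The concern holds in a limited form. As written, Exclusion 2 conditions the cohort partly on postoperative PN adherence, which overlaps the 30-day outcome window, and in this design it is probably applied with outcomes already recorded. The complication rate may be biased downward, upward or not at all. The size is f·d and cannot be derived from the documents; 1 to 3 points corresponds to assumed exclusions of 10-30% and an assumed 10-point risk difference, with negative differences bounded by the retained patients' rate. The plan should be changed on this point, although a material bias has not been demonstrated.

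The conflict between steps 4 and 5 is a separate wording error. It does not show that emergency patients are meant to be left out. It matters because a literal reading of the inclusion criterion could remove them.

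**What to change.** - Make the main analysis all consenting operated patients in whom perioperative PN was started, without Exclusion 2.
- Report the number of deviations from the step 4 course, with reasons where recorded.
- Give the per-protocol subset as a sensitivity analysis, counting PN stopped for death or a complication as adherent up to that point.
- State as a limitation that the consent requirement (Exclusion 1 and the telephone and signature step) may also select on outcome, and report how many patients were not contacted, refused or had died. Dropping Exclusion 2 does not remove this route.
- As a separate wording correction, limit step 5's statement on the timing of surgery to non-emergent patients, and change *after receiving* to *and received* in the inclusion criterion.

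The cost is a more heterogeneous main cohort and a little more tabulation. The dose-based part of the sensitivity analysis is possible only if the data sheet records dose, and reasons for stopping can be reported only where they were entered; the text available does not show whether either was. The main cohort also remains conditional on reaching surgery and on PN having been started, which the report should say.

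### The title asks whether perioperative PN affects outcome, but every included patient received PN, so the study can only describe outcomes

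*Combined protocol and SAP*

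**What the plan says.** The title begins "DOES PERI-OPERATIVE PARENTERAL NUTRITION" and goes on to ask about an effect on outcome in major abdominal surgery. It is the only study question in the text available; no separate objective or hypothesis appears there.

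The rules on who enters the study are these:

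- Inclusion criteria: "All patients who underwent major gastrointestinal surgery after receiving perioperative TPN".
- Exclusion criteria, item 2: "Perioperative TPN was not given as per the protocol".
- Data collection: the department sheet covers all major gastrointestinal operations, but "we will only select those cases who received perioperative TPN".

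PN was given by indication. Study Procedure 3 says "All the patients who were found to have malnutrition or were at severe risk of nutrition deficiency were given preoperative PN". Timing varied with urgency under Study Procedure 4: "In those patients who required emergency surgery, PN was given in postoperative period until resumption of oral feeding", whereas "In non-emergent cases where surgery could be delayed for 5 days, PN was given for 5 days preoperatively" and PN then continued after the operation.

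The Data Analysis Technique section names chi-square and Fisher tests for categorical data and univariate linear regression for association, without naming a grouping variable. It promises descriptive reporting and a comparison of the final result with studies in the Literature Review. The sample size of 143 is a one-group precision calculation for the prevalence of malnutrition.

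**The concern.** A question about whether a treatment affects outcome needs at least one group that did not receive it, or a defended external substitute. Here exposure is fixed by selection, and nothing in the plan stands in for the missing group.

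The risk lies in the reporting. With an effect question in the title and a set of significance tests in the analysis section, a reader could take an uncontrolled complication rate, or an informal comparison with published rates, as evidence for or against perioperative PN. No later analysis of the selected patients can repair this.

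**Working it through.** **1. The plan's own figure.** Inputs from the Sample Size section: Z² = 3.84, p = 0.24, q = 0.76, d = 0.07.

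n = Z²pq/d² = 3.84 × 0.24 × 0.76 / 0.0049 = 142.94, rounded up to 143. The stated figure is reproduced. The formula has one group and contains no effect size, power or allocation ratio, so it gives no basis for a comparison.

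**2. The PN versus no-PN contrast.** Let p₁ and p₀ be the outcome proportions with and without PN, and n₁ and n₀ the group sizes. The standard error of the difference is

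√[p₁(1 − p₁)/n₁ + p₀(1 − p₀)/n₀].

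The selection rules give n₀ = 0, so p₀ is never observed and the second term is undefined. Raising n₁ does not help. The planned methods meet the same limit: a table of PN by outcome has an empty row, so chi-square and Fisher tests have nothing to compare, and in a regression a PN indicator that equals 1 for everyone cannot be separated from the intercept.

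**3. Possible substitutes in the plan.**

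- *PN timing.* Under Study Procedure 4, postoperative PN goes with emergency surgery, and preoperative plus postoperative PN goes with non-emergent surgery. A timing comparison would also be a comparison of urgency, and both groups received PN.
- *Published studies.* The Data Analysis Technique section gives no method, matching or adjustment for this comparison, and the populations may differ.

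Neither identifies the effect of PN against none.

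**4. What the design can deliver.** The documents give no outcome rate, so the rates below are assumptions, and 143 is the calculated target, not a count of PN recipients. The Wilson 95% interval for x events in n patients is

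[x + z²/2 ± z√(x(n − x)/n + z²/4)] / (n + z²), with z = 1.96.

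For x = 43 and n = 143, the centre is (43 + 1.92)/146.84 = 0.306 and the half-width is 1.96 × √(30.07 + 0.96)/146.84 = 0.074.

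| Assumed events | Proportion | 95% CI | Width (points) |
|---|---|---|---|
| 29/143 | 20.3% | 14.5% to 27.6% | 13.1 |
| 43/143 | 30.1% | 23.2% to 38.0% | 14.9 |
| 57/143 | 39.9% | 32.2% to 48.0% | 15.8 |

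These widths do not measure the defect, which is the absence of a comparator. They show the precision of the descriptive result that remains available.

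**The case against.** The strongest reply is that this is a fault of the title alone. The body of the plan is already largely descriptive: a one-group sample size, categorical variables as proportions, descriptive reporting. It never says that the tests will compare PN with no PN, and associations within PN recipients are a legitimate use of them. Conclusions have not been written, and an objectives section may exist outside the text available.

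Much of this is fair. The tests are not wrong in themselves. But the title poses the only question available, and it will frame the conclusions. That the body is descriptive is a reason to align the title with it.

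Three narrower points also stand, without altering the conclusion:

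- Exclusion item 2 may refer to TPN given with deviations, not to TPN never given. The inclusion criterion and the selection rule settle the matter without it.
- The link between timing and urgency is less clean than Study Procedure 4 suggests. Study Procedure 5 has all patients operated on from the fifth day of admission, Study Procedure 3 has all at-risk patients receiving preoperative PN, and the inclusion criterion requires surgery after TPN. How emergency cases fit, and whether they are eligible, is unclear; these passages must be reconciled.
- No primary outcome is named, so 30-day complications are one describable outcome, not necessarily the intended one.

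**Conclusion.** The concern holds. Under the stated selection rules the number of patients without PN is zero, so the effect in the title cannot be estimated at any sample size. This follows from the inclusion criterion and the Data collection rule and needs no outside assumption.

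The study can describe outcomes in PN recipients, with 95% intervals about 13 to 16 points wide for complication rates of roughly 20% to 40%, if 143 patients are analysed. It cannot support a statement that PN improved, worsened or left outcome unchanged. Because this governs what the study may conclude, it should be corrected before results are reported. It would need revisiting only if a control group or a method for the external comparison is defined in text not available here.

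**What to change.** Restate the title, any objective and the conclusions as descriptive, for example: 30-day Clavien-Dindo complications in patients receiving perioperative PN, with 95% confidence intervals. If another outcome is the main one, name that instead. In the Data Analysis Technique section:

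- add confidence intervals to the outcome proportions;
- name the factors to be related to outcome within PN recipients;
- report emergency and non-emergent cases separately as description, once the passages on their PN timing and eligibility are reconciled;
- present the literature comparison as context only, and state that no conclusion about an effect of PN will be drawn.

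The cost is wording and a few intervals. Since the document carries an approval date, a changed title may also need notifying to the IRC. The price is a weaker claim, but one that the data can support.

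Keeping the effect question would be a different and expensive study. It would need non-PN patients from the department sheet with nutritional covariates recorded (Annex I is not in the text available), adjustment for confounding, its own sample size, IRC cover, and phone contact and a signed form for each added patient back to 2017, since Study Procedure 1 says "After signing the consent, the patient's data will be recruited in this study". It would also need overlap in nutritional status between PN and non-PN patients, which is doubtful if all malnourished or severe-risk patients received PN. Without overlap, only the descriptive restatement is defensible.

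### Data enter only after a signed consent sought after ethics clearance, so inclusion can depend on being reachable, and on survival if relatives may not sign

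*Combined protocol and SAP*

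**What the plan says.** In the combined protocol and SAP, Study Procedure 1 (Consent) sets out the route into the study in order:

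- Contact follows ethics clearance: "After obtaining ethical clearance from the IRC, those patients that fulfill the inclusion criteria will be offered detailed printed information about the proposed study".
- Because the study looks back, "phone calls will be done to the patients and their relatives for consent".
- The signing step is: "Patients agreeing to take part in the study will be requested to sign the consent form".
- Data follow the signature: "After signing the consent, the patient's data will be recruited in this study".

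The Ethical consideration section says that "verbal and written consent were obtained from the patient". That is in the past tense, yet the same section places ethics approval in the future.

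Under Research Design, sampling is called consecutive, and the inclusion criterion covers every patient who had major gastrointestinal surgery after perioperative TPN. There are two exclusions: refusal, and TPN not given per protocol. The period is given as "Duration of study: 2017, January 1st to 2022, August 31st", and the first page carries "Approval Date: 21st November, 2022".

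Study Procedure 6 (Complications) grades complications from records kept to 30 days after surgery. The Data Analysis Technique section compares the final result with studies from the literature review.

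**The concern.** The criteria and the consent procedure define different samples. A patient who has died or cannot be traced meets the inclusion criterion and neither refuses nor breaches the TPN protocol. As written, that patient may still not enter, because entry needs a signature. The signature is sought after the 30-day outcome has happened, so whether a patient is included can be related to that outcome.

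The title asks about an effect on outcome, and no control group is described. Outcome-related selection would therefore not be offset by a comparison group selected in the same way, and it would carry into the comparison with published studies. No count of eligible, unreachable or included patients is planned, so a reader could not judge how far the sample departs from the consecutive series.

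**Working it through.** **1. The plan's own figure.** 3.84 × 0.24 × 0.76 / 0.07² = 142.94, rounded up to 143. The sample size reproduces. It makes no allowance for non-contact or refusal. It is used below only as a convenient number of included patients.

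**2. Dates.** The inputs are the study period and the approval date on the first page. The document does not say whose approval this is. I assume that consent was sought no earlier than that date.

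- The last 30-day window closes on 31 August 2022 + 30 days = 30 September 2022.
- From 30 September to 21 November 2022 is 52 days.
- From 31 August to 21 November 2022 is 82 days. This is the minimum delay for a patient operated on the last day.
- From 1 January 2017 to 21 November 2022 is 2150 days, or 2150 / 365.25 = 5.9 years. This is the minimum delay for a patient operated on the first day.

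Under the assumption, every 30-day window had closed before consent could start.

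**3. Who can enter, as written.**

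| Patient | Meets a listed exclusion? | Can pass the signature step? |
|---|---|---|
| Alive, reached, agrees | No | Yes |
| Alive, reached, refuses | Yes | No |
| Cannot be reached, nor any relative | No | No |
| Deceased, relative reached and agrees | No | Unclear: relatives are phoned, only patients are said to sign |

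The last two rows are where the criteria and the procedure part.

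**4. Illustration of the effect.** The documents give no death, complication or consent rate, so every rate here is assumed. Death is used because it decides whether a patient can sign; the plan does not name mortality as a separate outcome. With true rate m, share cs of survivors included and share cd of deceased patients included:

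observed rate = m·cd / (m·cd + (1 − m)·cs)

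For m = 0.05, cs = 0.8, cd = 0.5: 0.025 / (0.025 + 0.760) = 3.2%. For cs = 0.6, cd = 0.8: 0.040 / (0.040 + 0.570) = 6.6%.

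| Assumed true rate | cs 0.8, cd 0.5 | cs = cd | cs 0.6, cd 0.8 | cd = 0 (only patients may sign) |
|---|---|---|---|---|
| 2% | 1.3% | 2.0% | 2.6% | 0% |
| 5% | 3.2% | 5.0% | 6.6% | 0% |
| 10% | 6.5% | 10.0% | 12.9% | 0% |

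The error can go either way, and it vanishes when the two shares are equal. The same formula applies to any complication if the shares are read as inclusion with and without it.

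**5. What counts would add.** With x events among 143 included and N eligible, the rate among all eligible lies between x/N and (x + N − 143)/N. With an assumed x = 7:

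- N = 179 (143/179 = 80% included): 7/179 = 3.9% to 43/179 = 24.0%.
- N = 159 (143/159 = 90% included): 7/159 = 4.4% to 23/159 = 14.5%.

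The upper ends require every patient left out (36 or 16) to have had the event. They are bounds, not forecasts. They show that a reader who knows N can limit the possible error, and that one who does not cannot.

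**The case against.** The strongest reply is that relatives are phoned for the very purpose of consent, so the ordinary reading is that they can give it. The consent form is not in this copy and may carry a next-of-kin line. This stands. A reader might infer that 30-day deaths cannot enter and that observed mortality must be 0%. The documents do not support that, because it needs a patients-only reading which the calls to relatives weigh against. What remains is that the text does not say a relative's consent is enough.

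A reader might also infer that the plan has no rule for unreachable patients. In effect it has one: without a signature there is no entry. The fault is that this is absent from the exclusion list and that no numbers are to be reported.

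The timing is open to challenge too. Ethical consideration speaks of consent as already obtained, and the approval date has no named source. That makes the timing an assumption. The Consent section, however, places contact after clearance and gives the retrospective design as the reason for phoning. The 82 days and 5.9 years are minimum delays for the last and first days of the period, not the ends of a range.

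Finally, every rate in the illustration is assumed, and the plan also has within-cohort tests (chi-square, Fisher, univariate regression) on which no effect has been shown here. Both points are right, and they limit the conclusion to the complication results and their comparison with published studies.

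**Conclusion.** The concern holds in a limited form. Followed as written, inclusion can depend on reachability, and on survival if relatives may not sign. This conflicts with the claim of consecutive sampling and can bias the 30-day complication results. That the outcome windows had closed before consent began rests on consent starting no earlier than 21 November 2022; the gap is then at least 52 days.

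Neither the direction nor the size of any bias can be derived from the documents. A reader might infer that complications or deaths are bound to be under-counted. That follows only if deceased patients are included less often than survivors, which the plan does not establish. The point should be fixed, because it concerns who is in the sample and the remedy is cheap. It does not show that the results are wrong. Confidence is medium, mainly because the consent form cannot be seen.

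**What to change.** - Ask the ethics committee to waive consent for de-identified existing records of deceased and unreachable patients. Alternatively, ask it to accept next-of-kin consent for the deceased, if the form does not already do so.
- State the outcome in the Consent section, including who may sign and what happens when nobody can be reached. Align the exclusion list and the tense of the Ethical consideration section with it. Include the records so admitted in the main analysis.
- In either case, report the numbers eligible, contacted, unreachable, refusing and included. The departmental data sheet is said to hold all major operations, so it can supply the number eligible; the rest needs a contact log.
- Give outcomes of patients not included only in aggregate, and leave refusers out unless the ethics committee permits their use.
- If no waiver is granted, describe the sample as consenting patients and not as consecutive.

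The cost is one request to the ethics committee, a wording change and a short log kept during the phone calls.
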